11 ASSESSMENT OF EFFICACY

The primary and secondary efficacy analyses will be based on the independent centralized assessment of medical images. A detailed description of the process is provided in the Independent Review Charter.

11.1 Efficacy Variables

Primary endpoint

The primary endpoint is the PFS rate at 12 weeks, defined as the proportion of patients alive and progression-free at Week 12. Patients will be progression-free if they have no evidence of progressive disease (defined according to RECIST guidelines, version 1.1) from the start of treatment to Week 12.

Tumor response will be assessed at 6-week intervals during the first treatment cycle using the RECIST criteria version 1.1. Each patient will be assigned one of the following categories: 1) complete response (CR), 2) partial response (PR), 3) stable disease (SD), or 4) progressive disease (PD). Patients who died from any cause or discontinued the study for any reason without a post-screening or Week 12 tumor assessment will be considered as failing to respond to treatment.

Secondary efficacy endpoints

Secondary efficacy endpoints are as follows:

- Objective response rate, defined as the proportion of patients whose best overall response is either CR or PR according to RECIST version 1.1. The best overall response is the best response recorded during the first 12-week treatment cycle.
- Disease control rate, defined as the proportion of patients with a documented CR, PR and SD during the first 12-week treatment cycle according to RECIST version 1.1.
- Duration of overall tumor response, defined as the interval between the date of the first observation of tumor response (CR or PR) and the date of disease progression or death.
- Progression free survival, defined as the time from the date of first administration of study drug to objective tumor progression by RECIST version 1.1 or death due to any cause, whichever occurs first.
- Overall survival, defined as the time from the date of first administration of study drug to death from any cause.
- Time to progression, defined as the time from the date of first administration of study drug to objective tumor progression by RECIST version 1.1.

Patient Reported Outcome endpoint:

The PRO endpoint is as follows:

- European Organization for Research and Treatment of Cancer QLQ-C30 and the EORTC QLQ-LC13.

Pharmacokinetic endpoints:

For Stage 1, PK endpoints will be derived for intensively sampled PK profiles by non-compartmental methods and include:

- C_{\max} : peak concentration
- C_{trough} : trough plasma concentration
- T_{\max} : peak time
- AUC_{τ} : area under the plasma concentration-time curve over the 8-hour dosing interval
- $T_{1/2}$: terminal half-life
- V_z/F : apparent volume of distribution during elimination
- CL/F : apparent oral clearance
- $T_{1/2, \text{eff}}$: effective half-life

If possible, PK data from all patients will be analyzed using PopPK methods and *post hoc* estimates of antroquinonol exposure (i.e., C_{\max} , C_{trough} , and AUC_{τ}) will be computed for exploration of potential exposure-response relationships.

Tumor biomarkers:

Subgroup analyses will assess the predictive value of tumor biomarkers.

11.2 Efficacy Assessments

11.2.1 Tumor Measurement

Tumor assessment will be performed during the 12 week treatment period using computed tomography (CT) scan or magnetic resonance imaging (MRI) according to RECIST guideline, version 1.1 (see [Appendix 1](#)) at the Screening Visit, Visit 4 (42), and Visit 6 (84). Tumor assessments will be performed every 12 weeks during the Extension Phase. The tumor assessment does not need to be performed at the EOS Visit if this was conducted at the Day 84 Visit. For patients participating in the Extension Phase, the tumor assessment does not need to be performed at the EOS Visit if it has been assessed within 8 weeks of the EOS Visit. The preferred scan is a CT of the chest, abdomen, and pelvis, performed with IV contrast. If patients have a contraindication to iodinated contrast, such as a documented allergy or impaired renal function, a non-contrast CT of the chest and MRI of the abdomen and pelvis is permitted (MRI preferably with gadolinium contrast, though this may be omitted if renal impairment is severe). Imaging evaluation at the Screening Visit must be performed within 14 (\pm 7) days of the date of first administration of study drug.

The same method of assessment will be used at each tumor assessment visit as used at the baseline visit.

11.2.2 Clinical Response – Solid Tumors

Clinical response will be evaluated according to RECIST criteria²⁵ in evaluable patients, by comparing the measurements and number of target lesions at baseline and during the study.

The RECIST version 1.1 guidelines for measurable, non-measurable, target and non-target lesions and the objective tumor response criteria are in [Appendix 1](#).

11.2.3 Tumor Biomarkers

Formalin fixed paraffin embedded (FFPE) tumor tissue will be submitted for analysis of tumor biomarkers. Next-generation sequencing will be used to screen a panel of 236 genes commonly mutated in tumors, including KRAS, EGFR, and ALK. Patients will be stratified according to KRAS mutation status to test for possible differences in sensitivity/resistance to the study drug. In addition, selected samples may also have ALK and ROS1 status determined by immunohistochemistry.

Refer to the Laboratory Manual for details of the mutation assays, and instructions for sample collection, handling, and shipment.

12 PHARMACOKINETICS

12.1 Pharmacokinetic Sampling

PK sampling will be performed on Day 0 and Day 28 in all patients enrolled in Stage 1 at the following time points:

Day 0: (Approximately 5 mL per sample, 60 mL in total) 30 minutes prior to and 0.5, 1, 2, 3, 4, 6, and 8 hours after the first dose.

Day 28: (Approximately 5 mL per sample, 60 mL in total) immediately before and 0.5, 1, 2, 3, 4, 6, and 8 hours after the first dose on Day 28.

Sparse PK sampling will be performed on Days 28, 42, and 56 in all patients enrolled in Stage 2. At least two samples will be collected on each occasion, one of which will be a trough concentration (30 minutes prior to the first dose on Days 28, 42, and 56 and approximately 8 hours after the last dose on the prior day). At least one sample per patient will be timed to coincide with the peak concentration (3 hours after the first dose). The remainder may be taken at any time during the dosing interval.

Each blood sample will be analyzed for antroquinonol plasma concentration to determine PK parameters after administration of antroquinonol using a fully validated bioanalytical method (a copy of the analytical method validation report and bioanalytical report will be included in the clinical study report).

12.2 Pharmacokinetic Sampling Procedures

12.2.1 Blood Samples

Samples of venous blood will be obtained in 5 mL sodium heparin Vacutainer[®] tubes at the sample times listed above in Section 12.1. Immediately after collection the tube will be gently inverted 8 to 10 times to mix the anticoagulant with the blood sample. All samples will be processed and placed into a freezer within one (1) hour after collection. The plasma fraction will be separated by placing the collection tube into a refrigerated centrifuge (4°C) for 10 minutes at 3000 rpm. The plasma fraction will be withdrawn by pipette and divided into two polypropylene freezing tubes (with each tube receiving approximately equal aliquots). All sample collection and freezing tubes will be clearly labeled with the patient number, the study period, and the collection time. Labels will be fixed to freezing tubes in a manner that will prevent the label from becoming detached after freezing. All plasma samples will be placed into a freezer at -70°C within 1 hour after collection.

12.2.2 Sample Storage and Shipping

All plasma samples will be stored frozen (at -70°C) until they are shipped to the Central Laboratory Facility. Prior to shipping, the samples will be packed into thermal insulated containers and packed in sufficient dry ice to assure they remain frozen, and are protected from breakage during shipment. Samples will be shipped by overnight, priority courier. The samples will be divided into two shipments, each containing one aliquot of plasma for each time point. After receipt of verification that the first shipment was received by the Central

Laboratory Facility in good condition, the second shipment will be sent to the Central Laboratory Facility.

Samples will be shipped monthly to the Central Laboratory Facility. The shipping address and contact information will be provided in a separate document.

12.2.3 Analytical Methodology

The concentration of study drug will be determined from the plasma samples using a validated analytical method. Details of the method validation and sample analysis will be included in the final clinical study report.

13 ASSESSMENT OF SAFETY

Safety will be assessed based on AEs, clinical laboratory results (routine hematology and biochemistry), physical examination, vital signs, and ECG recording.

13.1 Height and Weight

Height is to be measured for the patient not wearing shoes at the Screening Visit and will be rounded to the nearest centimeter. Weight and BMI will be measured at Screening Visit only.

13.2 Demographics

Demographic data including date of birth and gender information will be obtained at Screening.

13.3 Medical History

General medical history should be recorded at the Screening Visit. The medical history should include procedural and surgical history within the past year. Cancer history should be recorded on a life-time basis.

13.4 Previous and Concomitant Medications

All previous medications taken by the patient during the 6-week period prior to study enrollment should be recorded at the Screening Visit. Cancer therapies should be recorded on a life-time basis. All concomitant medications starting from enrollment of patients should be recorded.

13.5 Physical Examination

Patients will be examined at every visit by standard physical examination including general appearance, skin, eyes, ear/nose/throat, head and neck, heart, chest and lungs, abdomen, extremities, lymph nodes, musculoskeletal, neurological, and other body systems if applicable for describing the status of their health.

13.6 Vital Signs

Vital signs will be measured for all patients at every visit and include blood pressure, pulse rate, respiratory rate, and body temperature.

13.7 Electrocardiograms

Electrocardiograms will be performed at every visit, except Visit 2. The evaluation items for all ECGs will include heart rate, QRS complex, QT interval, QTc, and RR intervals. At Screening the investigator should examine the ECG for signs of cardiac disease that could exclude the patient from the study. An assessment of normal or abnormal will be recorded and if the ECG is considered abnormal, the abnormality will be documented on the eCRF.

13.8 Eastern Cooperative Oncology Group Performance Status

The performance status of patients will be graded by their ECOG performance status score at every visit, except Visit 2. The description of ECOG performance status scale is defined as follows:

- 0: Normal activity. Fully active, able to carry on all pre-disease performance without restriction.
- 1: Symptoms, but ambulatory. Restricted in physically strenuous activity, but ambulatory and able to carry out work of a light or sedentary nature (e.g., light housework, office work).
- 2: In bed <50% of the time. Ambulatory and capable of all self-care, but unable to carry out any work activities. Up and about more than 50% of waking hours.
- 3: In bed >50% of the time. Capable of only limited self-care, confined to bed or chair more than 50% of waking hours.
- 4: 100% bedridden. Completely disabled. Cannot carry on any self-care. Totally confined to bed or chair.
- 5: Dead.

13.9 Laboratory Variables

Blood laboratory tests including red blood cells, white blood cells with differential counts, platelet count, hemoglobin, hematocrit, sodium, potassium, calcium, magnesium, phosphorus, glucose, blood urea nitrogen, creatinine, uric acid, albumin, total protein, alkaline phosphatase, ALT, AST, total bilirubin, gamma glutamyltransferase, and C-reactive protein will be taken at every visit. Urinalysis including pH, erythrocyte, leukocyte, glucose, and protein will be conducted at the same visits at which blood laboratory tests are performed. All tests will be performed at the Central Laboratory Facility.

All Screening laboratory results must be available and reviewed before the patient receives the first dose of study drug at Visit 1 (Day 0). After the test results are evaluated, the investigators should judge whether patients are still eligible to stay in the study. Significant abnormal values occurring during the study will be followed until repeat test results return to normal, stabilize, or are no longer clinically significant.

13.10 Adverse Events

An AE is any untoward medical occurrence in a patient during participation in the study, regardless of the relationship of the occurrence to the treatment with the study drug. An AE can be any unfavorable sign or symptom or diagnosed new disease or deterioration of existing chronic or intermittent diseases, significantly unexpected deteriorated condition of the study indication, which is associated with the use of the study drug. Abnormal can be considered as aforementioned signs and can be considered an AE. However, hospital admissions and/or surgical operations scheduled prior to the participation in this study for a pre-existing illness or disease to be performed during participation in this study are not to be considered an AE. The investigators are responsible for the detection, reporting, and documentation of AEs.

13.10.1 Disease-Related Events

A disease-related event is defined as an event that can be explained by the study indication. Considering the nature of the study patients to be late-stage cancer patients, the natural course of the disease leading to death or life-threatening conditions is considered as AEs or SAEs. The investigator must judge whether the event is a consequence or progression of the pre-existing disease(s). Disease-related events, like any other events that are life-threatening, or result in death, must be reported as SAEs.

13.10.2 Lack of Efficacy

Lack of efficacy is not to be considered as an AE. The signs and symptoms or clinical sequelae resulting from lack of efficacy will be reported if they fulfill the definitions of AE or SAE.

13.10.3 Clinical Laboratory Abnormalities

Abnormal laboratory findings and/or assessments that are judged by the investigator to be clinically significant will be reported as AEs or SAEs if they meet the definitions set forth. For the conditions that the abnormal laboratory and/or assessment findings are considered as the underlying disease-related, and are not unexpectedly worsened during the study, no AE or SAE should be reported.

13.10.4 Recording AEs and SAEs

All AEs and SAEs should be documented in the source documents and the relevant eCRF and SAE form when applicable. The investigator may be asked to provide photocopies of the medical records for completing the AE or SAE report. The medical records submitted to the relevant parties will be concealed of the patients' names. It is the responsibility of the investigator to report AEs or SAEs by diagnosis terminologies, if possible. When the diagnosis is possible for the reported AE or SAE, no signs and symptoms used to establish that particular diagnosis should be reported. The investigator will be asked to determine the severity and causality of each AE and SAE based on the investigator's clinical judgment. Five levels of intensity and two levels of causality are used to evaluate each AE and SAE as shown below:

Severity based on the National Cancer Institute (NCI) CTCAE version 4.03:

- Grade 1: Mild; asymptomatic or mild symptoms; clinical or diagnostic observations only; intervention not indicated.
- Grade 2: Moderate; minimal, local or non-invasive intervention indicated; limiting age-appropriate instrumental activities of daily living.
- Grade 3: Severe or medically significant but not immediately life-threatening; hospitalization or prolongation of hospitalization indicated; disabling; limiting self-care activities of daily living.
- Grade 4: Life-threatening consequences; urgent intervention indicated.
- Grade 5: Death related to AE.

*There is no direct relationship for severity and seriousness of an AE.

Causality:

- Possibly related: The suspected AE may follow a reasonable temporal sequence from test drug administration but could have been produced or mimicked by the patient's clinical state or by other modes of therapy concomitantly administered to the patient.
- Unrelated: Should be reserved for those events which occur prior to unrelated test drug administration (i.e., washout or single-masked placebo) or those events which cannot be even remotely related to study participation (e.g., injuries sustained in an automobile accident).

It is important for the investigators to take information of underlying diseases, concomitant drugs, and temporal relationship of the onset of the event to the time of dosing the study drug, and re-challenging outcomes, into account when making a causal relation decision. It is the investigators' responsibility to follow proactively the outcome of each AE until resolution or stabilization of the condition, alternative treatment for NSCLC is started, 6 months after last dose of study drug, or loss to follow-up, whichever occurs first. In the event of serious or study drug-related toxicities, the patient will be followed until resolution or stabilization. Safety follow-up data may be collected by telephone contact every 3 months after the EOS Visit.

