10.5 Dose Modification

The guidelines for dose modification and management of drug toxicity are as follows:

Table 10.1 Dose Modification and Management of Drug Toxicity Guidelines

Event	Grade	Management/Action
All non-hematologic and hematologic adverse events that are study drug-related	1 or 2	No change.
	3	Suspend treatment. Treatment may resume if toxicity is resolved to grade ≤ 1 or returns to baseline within 7 days. Treatment should resume at a reduced dose (100 mg t.i.d). If toxicity lasts more than 7 days, study drug will be permanently discontinued (subject to investigator and Medical Monitor agreement); if a patient experiences another grade ≥ 3 toxicity at the reduced dose, then study drug will be permanently discontinued.
	4	

Treatment may be withheld for up to 7 days due to study drug-related toxicities. Patients will be permanently discontinued from the study drug if treatment interruption is more than 7 days and the investigator and Medical Monitor consider that permanent cessation of study drug is necessary. If a patient resumes treatment before the end of a cycle, the patient will have to complete the rest of the treatment of that cycle.

When patients are suspected to experience Grade 3 or more AEs, they should contact the site as soon as possible for an appointment and bring back any unused study drug to the site. Treatment should only be withheld for nausea, vomiting, and diarrhea of Grade ≥ 3 if symptoms remain at Grade ≥ 3 despite adequate treatment. If dose modification is deemed necessary, the unused study drug will be retrieved and a new bottle with quantity of study drugs calculated based on the modified dose will be dispensed. Sufficient study drug should be dispensed for the period from the day of dose modification to the next dispensing visit.

The quantity given will be recorded in the eCRF and the drug accountability log. At the time the patient returns the unused study drug, they will be counted at the site and recorded in the eCRF. The dates and durations of any dosing interruptions will be recorded in the eCRF.

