14.2.4 Safety Analysis

All patients who are treated with at least one dose of study drug will be evaluated for safety. Safety data will be summarized for the overall (unselected) population and within-stratum. There will be no formal statistical analysis of safety data. Demographic and Screening data will be listed and summarized, as appropriate. All AEs will be coded using the Medical Dictionary for Regulatory Activities (MedDRA), graded using the NCI CTCAE version 4.03 and listed by patient. Treatment-emergent AEs will be summarized by treatment, severity and causal relationship to study drug. Any serious AEs will be listed separately.

System organ class and preferred terms within each body system will be used for frequency summaries. CTC grades for clinical laboratory data will be derived, and changes in CTC grades will be summarized by visit. Vital signs and ECG data will be listed by patient and summarized, as appropriate.

Safety data followed up during the Extension Phase will be analyzed where all patients will complete the Extension Phase.

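### The two causality definitions in Section 13.10.4 do not fit this single-arm trial: read literally, an on-drug event judged due to NSCLC can only be coded *Possibly related*

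*Protocol*

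**What the plan says.** Protocol Section 13.10.4 states: "Five levels of intensity and two levels of causality are used to evaluate each AE and SAE".

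- *Possibly related* is an event that may follow drug administration in a reasonable time sequence but "could have been produced or mimicked by the" patient's clinical state or by concomitant therapy.
- *Unrelated* has two limbs. The first is "Unrelated: Should be reserved for those events which occur prior to unrelated test drug administration (i.e., washout or single-masked placebo"). The second is "those events which cannot be even remotely related to study participation (e.g., injuries sustained in an automobile accident").

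The same section leaves causality to the investigator's clinical judgment and asks that underlying disease, concomitant drugs, timing and rechallenge be weighed. Section 13.10.1 adds, for disease-related events: "The investigator must judge whether the event is a consequence or progression of the pre-existing disease(s"). It also requires disease events that are fatal or life-threatening to be reported as SAEs.

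The causality flag is then used in Section 14.2.4: "Treatment-emergent AEs will be summarized by treatment, severity and causal relationship to study drug". Table 10.1 in Section 10.5 applies to "All non-hematologic and hematologic adverse events that are study drug-related". Section 13.10.4 has its own follow-up rule for drug-related toxicities, and Section 13.10.5 sets no time limit on collecting SAEs considered related to the drug.

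**The concern.** The definitions appear to have been written for another kind of trial. The *Unrelated* sentence is garbled (it speaks of an unrelated test drug), and its single-masked placebo example has no counterpart in a single-arm, open-label study (Section 9.1.1). The more serious problem is the pairing of the two levels. One is reserved for a very narrow set of events, and the other includes, by its own terms, events with a plausible disease explanation. In stage IV NSCLC that describes much of what will be reported on treatment.

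Sections 13.10.1 and 13.10.4 ask the investigator to decide whether the disease is the cause, but the scale has no place to record that answer. Two investigators who agree on the clinical facts could code the same event differently, depending on whether they follow the definitions or the guidance below them. What is at stake is the meaning of the relatedness table, and of every rule that refers to drug-related events.

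**Working it through.** No arithmetic applies: the point rests on no rate, sample size or power figure. The check is to run typical events through the definitions.

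**Inputs**
- Two levels only (Section 13.10.4).
- Single-arm, open-label, no placebo phase (Section 9.1.1).
- AEs followed from informed consent (Table 9.1, footnote 12), with Screening of up to 42 days (Section 9.1.1), so events before the first dose are possible.
- Signs and symptoms of lack of efficacy are reported if they meet the AE definition (Section 13.10.2). Laboratory findings due to the disease that do not worsen unexpectedly are not reported (Section 13.10.3). Disease events therefore enter the AE data, apart from that laboratory exception.

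**Test events**
1. *Effusion worsens during Screening.* Onset is before drug, so the first limb applies: *Unrelated*.
2. *Injury in a road accident on drug.* The second limb applies: *Unrelated*.
3. *Dyspnea from a growing effusion in Week 5, judged by the investigator to be due to NSCLC.* Onset is after the first dose, so the first limb fails. The second limb demands "those events which cannot be even remotely related to study participation". That standard is far stricter than the drug not being the likely cause, and it is set against study participation, not the drug. A disease event during treatment can rarely meet it. The timing is compatible and the clinical state could have produced the event, so both parts of *Possibly related* are met: *Possibly related*.
4. *Diarrhea starting soon after the first dose, with no other explanation.* *Possibly related*.

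Events 3 and 4 receive the same code, although Section 13.10.1 has the investigator reach opposite conclusions about them.

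**Effect on the planned table.** Section 14.2.4 summarizes treatment-emergent AEs by relationship. The protocol does not define treatment-emergent. If it has its usual meaning of onset after the first dose (an assumption), event 1 drops out of the table and the first limb contributes nothing to it. Only the second limb could then fill the *Unrelated* row.

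**Terms used elsewhere.** Section 10.5 and the follow-up rule in 13.10.4 speak of study drug-related events, and Section 13.10.5 of SAEs considered related. No section says which scale level these mean. *Possibly related* is the only level other than *Unrelated*, so the natural reading is that they are the same, but that is an inference.

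**The case against.** The strongest reply is that the literal reading is not compelled. Section 13.10.4 starts from clinical judgment, requires underlying disease to be weighed, and offers the accident only as an example. An investigator could reasonably code event 3 *Unrelated*. The pre-drug limb is not empty either: AEs are collected from consent, and the treatment-free intervals in Section 9.3.2 work much like a washout. Broad attribution is also a defensible caution after a 13-patient Phase 1 study.

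Much of this stands. It shows that the text supports two codings, not that it supports the right one. The word reserved in the definition limits when *Unrelated* may be used, and the guidance to weigh disease does not widen it. If broad attribution is intended, the judgment required in Section 13.10.1 has no outlet.

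Three stronger readings are tempting, and the documents do not support them.
- *The safety objective is defeated.* The Synopsis defines the safety endpoints as the incidence of reported AEs and abnormal laboratory tests, whatever the cause. Section 14.2.4 also tabulates by severity, system organ class and preferred term, and Section 8.3 plans exposure-safety exploration.
- *Misattributed events trigger dose changes, cause primary-endpoint failures and cost power.* Table 10.1 requires no change at Grade 1 or 2, so any effect is limited to Grade 3 or 4 and depends on the inferred mapping of terms. Stopping drug alone is not failure under Section 14.2.2.1, and the End of Study visit includes a tumor assessment unless one was done at Day 84. Nothing in the protocol gives a rate at which would-be successes would be lost.
- *Re-scoring the Phase 1 events measures the problem.* Section 7.4 reports that none of the deaths, SAEs or AEs leading to discontinuation was related. It gives too little on onset and clinical detail to re-score them, and it also reports treatment-related events in all 13 patients.

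**Conclusion.** The point holds as a misfit of definitions with a real but limited consequence. Followed as written, Section 13.10.4 pushes on-drug NSCLC events into *Possibly related*, against the disease judgment in 13.10.1 and the weighing of disease in 13.10.4 itself. The summary by causal relationship is degraded, and the meaning of study drug-related in Sections 10.5, 13.10.4 and 13.10.5 is left open. The all-causality safety endpoints stand, and no effect on the primary endpoint is shown.

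The number of events affected cannot be estimated from the documents. The design rates of 15% to 40% progression-free at Week 12 imply that 60% to 85% of patients are not, but those are endpoint failures, not AEs. The conclusion assumes that investigators apply the definitions as worded; where they follow the guidance instead, the damage is inconsistent coding between sites. Because the definition governs how data are recorded, an analysis plan cannot repair it afterwards.

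**What to change.** - **Redefine the two levels in Section 13.10.4.** *Related*: a reasonable possibility that antroquinonol caused the event. *Unrelated*: no reasonable possibility, for example onset before the first dose, or an event the investigator attributes to NSCLC, another illness, a concomitant treatment or a procedure. Delete the washout and single-masked placebo text.
- **Reconcile Sections 10.5, 13.10.1, 13.10.4 and 13.10.5** so that study drug-related has one stated meaning against the scale. The new definition could change which events meet the condition of Table 10.1. How it should bear on that table is for the sponsor to decide, and no dose or clinical rule is proposed here.
- **Keep all-causality tables as the main safety display**, with the relatedness summary as support.

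The cost is a protocol wording change and eCRF completion guidance. For events already coded under the present text, the report should say which definition applied. The downside is that narrower attribution leans more on investigator judgment and could under-attribute some drug toxicity, which is why the all-causality tables should lead.
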